## ***Primary analyses***

Group comparisons will be tested with a linear mixed-effects model with the percentage-change from baseline to months 6 and 12 in aBMD at the total hip and femoral neck. Baseline aBMD at the total hip and femoral neck, study visit, ambulatory status measured by WISCI and interaction of WISCI with visit will be fitted as random factors. aBMD by group interaction will be considered statistically significant at  $p < 0.05$ . Raw effect sizes will be calculated as differences between groups at each time point. Multiplicity will be handled by utilizing a fixed-sequence approach to testing, with initial analysis of total hip ( $\alpha=0.05$ ) and if successful followed by femoral neck ( $\alpha=0.05$ ).

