3.1. Overview

This is a 2 year, randomized, double-blind placebo-controlled study of zoledronic acid to evaluate its efficacy and safety for the prevention of bone loss and maintenance of bone strength in individuals with recent onset SCI (see diagram below). Subjects will be randomized at the baseline visit to receive either zoledronic acid or placebo. At the end of the first year of the study, each treatment group will be re-randomized to either zoledronic acid or placebo to evaluate the durability of response to zoledronic acid and the utility of serum bone markers to guide therapeutic decision making. DXA imaging, CT imaging of knee and bone markers will be obtained at baseline, 3 months, 6 months, 12 months, 18 months and 24 months. CT imaging of hip will be obtained at baseline, 6 months, 12 months, and 24 months.

3.2. Centers and enrollment goal:

This will be a single center study. 60 subjects meeting inclusion and exclusion criteria will be enrolled at Northwestern University. University of Calgary (UC) will act as a site for de-identified data analysis of CT scans. No subjects will be enrolled and no visits will take place at UC.

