3.6. Study Variables

Clinical and Demographic Information

Clinical and demographic information will be obtained by personal interview and, if necessary, review of medical records. This information will include a complete medical history, including demographic information, with specific emphasis on bone-related issues (history of fracture, endocrinopathy, vitamin D intake, etc.) utilizing a bone health questionnaire used by our group to acquire baseline data for our in-house bone registry (Spinal Cord Injury & Lifestyle Information Form). They will also complete the Spinal Cord Independence Measure^{77,78} (SCIM) prior to randomization. In order to assess ambulatory ability and status, participants will be asked to complete the Walking Index for Spinal Cord Injury⁷⁹ at each visit. This is a validated instrument to assess activity levels that affect bone loading and may be expected to have an impact on the effects of treatment that participants will be receiving.

DXA BMD

BMD will be determined by DXA at various skeletal sites (bilateral total hip, bilateral femoral neck, spine, non-dominant forearm, non-dominant knee (distal femur, proximal tibia), total body). The DXA scans will be performed at Baseline, 3 mos, 6 mos, 12 mos, 18 mos, and 24 mos by a trained DXA technician from our study team using a Hologic QDR 4500A densitometer. DXA scans performed at SRAlab will be done on the Hologic Horizon DXA scanner and will be performed by a SRAlab DXA technician, with oversight by our study team. All subjects who have their baseline scan at SRAlab will continue their follow up on the same machine. Whole body and forearm scans will be optional scans as they do not contribute to the primary or secondary study endpoints. Standard acquisition and analysis protocols will be used to quantify areal bone mineral density (aBMD) of all skeletal sites.

We have had extensive experience in DXA imaging of individuals with SCI. There have been no technical problems with DXA imaging though positioning has been challenging for some participants due to contractures and spasticity, and orthopedic hardware has also prevented the full set of images from being obtained. For those individuals with obstacles in obtaining images of the non-dominant knee and/or forearm, the dominant extremity will be used. As much as possible, positioning is reproduced at subsequent visits to allow appropriate comparisons.

CT determined bone parameters.

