## Overview

This is a 2-year, randomized, double-blind placebo-controlled study of zoledronic acid to evaluate its efficacy and safety for the prevention of bone loss and maintenance of bone strength in individuals with recent onset SCI (see protocol). Subjects were randomized at the baseline visit to receive either zoledronic acid or placebo. At the end of the first year of the study, each treatment group was re-randomized to either zoledronic acid or placebo to evaluate the durability of response to zoledronic acid and the utility of serum bone markers to guide therapeutic decision making. DXA imaging, CT imaging of knee and bone markers were obtained at baseline, 3 months, 6 months, 12 months, 18 months and 24 months. CT imaging of the hip was obtained at baseline, 6 months, 12 months, and 24 months.

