## Statistical Methods

### *Diagnostics*

All variables will be plotted to examine distribution shapes as well as percentage of missing values. The mixed modelling proposed below uses both all available observations without deleting cases and imputed data. Residuals will be examined for each model fitted in case of unexpected violations of assumptions. Analysis will be performed as ITT (intention to treat): patients will be analyzed according to the treatment arm to which they were randomized.

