## ***Missing Data***

Missing data will primarily be inputted by maximum likelihood estimation using a mixed effects model. A sensitivity analysis will be done latter, by using a multiple imputation methodology before modelling. Here, imputation of missing data will be based on sampling from a normal distribution using a mean value of the subjects' last observed value and standard deviation (over treatment groups) of the observed data at the missing endpoint (3, 6, or 12 months). This is a multiple imputation version of Last Observation Carried Forward (LOCF) single imputation method. Note, a subject's last observation may be the Baseline observation. One hundred imputed datasets will be used in this analysis. The linear mixed-effects model described below will be used for each imputation dataset, and the overall results will be calculated to take account of the variability both within and between imputation datasets using standard methods (Little & Rubin, 2002).

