## Analysis Plan Summary

Endpoint	Statistical Method	Model/Covariates	Missing Data	Objective
% Change from Baseline at 6,12 months with total hip and femoral neck aBMD, DXA	MEM	Baseline total hip/ femoral neck aBMD, visit, WISCI score; (subjects as random effects)	MLE	Primary Analysis
% Change from Baseline at 6,12 months with total hip aBMD, DXA	MEM	Baseline total hip aBMD, visit, WISCI score; (subjects as random effects)	Multiple Imputation	Sensitivity Analysis
% Change from Baseline at 6,12 months with total hip aBMD, DXA (a)	MEM	Baseline total hip aBMD, visit, WISCI score, (subjects as random effects)	MLE	Secondary, Interaction Analysis
% Change from Baseline at 6, 12 months with femoral neck aBMD, DXA (b)	MEM	Baseline total hip aBMD, visit, WISCI score; (subjects as random effects)	MLE	Secondary Analysis
% Change from Baseline at 6,12, months with QCT Int.vBMC Femoral Epiphysis (b)	MEM	Baseline total hip aBMD, visit, WISCI score; (subjects as random effects)	MLE	Secondary Analysis
% Change from Baseline at 6,12, QCT Int.vBMC Femoral Metaphysis (b)	MEM	Baseline total hip aBMD, visit, WISCI score; (subjects as random effects)	MLE	Secondary Analysis
% Change from Baseline at 24 months with total hip aBMD, DXA (c)	MEM	Baseline total hip aBMD, visit, WISCI score; (subjects as random effects)	MLE	Secondary Analysis
% Change from Baseline at 24 months with	MEM	Baseline total hip aBMD, visit, WISCI	MLE	Secondary Analysis

femoral neck aBMD, DXA (c)		score; (subjects as random effects)		
% Change from Baseline at 24 months with QCT Int.vBMC Femoral Epiphysis (c)	MEM	Baseline total hip aBMD, visit, WISCI score; (subjects as random effects)	MLE	Secondary Analysis
% Change from Baseline at 24 months with QCT Int.vBMC Femoral Methaphysis (c)	MEM	Baseline total hip BMD, visit, WISCI score; (subjects as random effects)	MLE	Secondary Analysis

(a) Secondary analysis phase 1: Interaction Analysis for primary endpoint with WISCI; (b) Secondary analysis phase 2: Secondary endpoints at 12 months; (c) Secondary analysis phase 3: Primary and Secondary endpoints at 24 months. aBMD (areal bone mineral density); MEM (mixed effects model); MLE (maximum likelihood estimates); WISCI (walking index for spinal cord injury).

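### The primary mixed model omits the scheduled month-3 DXA, so a participant whose only post-baseline scan is at month 3 adds nothing to the primary estimate

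*SAP*

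**What the plan says.** **Collection.** Protocol 3.1 states: "DXA imaging, CT imaging of knee and bone markers will be obtained at baseline, 3 months", and Protocol 3.6 repeats the DXA schedule: "The DXA scans will be performed at Baseline, 3 mos, 6 mos, 12 mos, 18 mos, and 24 mos". The SAP Overview reports the same visits in the past tense: "DXA imaging, CT imaging of knee and bone markers were obtained at baseline, 3 months, 6 months, 12 months, 18 months and 24 months". Protocol 7 makes attendance at month 3 desirable but not required, and allows a phone visit instead, so some participants will have no month-3 scan.

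**Primary model.** SAP, Primary analyses, uses the "percentage-change from baseline to months 6 and 12 in aBMD at the total hip and femoral neck". The Analysis Plan Summary agrees: "Change from Baseline at 6,12 months with total hip and femoral neck aBMD, DXA", with missing data handled by maximum likelihood.

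**Missing data.** SAP, Diagnostics, says the mixed modelling "uses both all available observations without deleting cases and imputed data" and that the analysis is by intention to treat. Under Missing Data, the sensitivity imputation draws each value from a normal distribution centred on the participant's last observation. Its standard deviation is that of the "of the observed data at the missing endpoint (3, 6, or 12 months" after baseline. SAP, Sensitivity analyses, then repeats the primary model on the imputed data.

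**The concern.** A likelihood-based mixed model gives valid results under missing at random, but only conditional on what is in the model. A month-3 change that was measured and left out can neither inform the estimate nor account for drop-out related to it. A participant scanned at baseline and month 3 who then leaves is randomized, treated and measured, yet absent from the primary estimate. That sits badly with the statement in Diagnostics. The imputation rule also names a month-3 endpoint for which neither the primary model nor its imputed repeat has an outcome.

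At stake are some precision, some protection against bias, and a clean comparison between the primary and sensitivity analyses. As planned, the two rest on different participants, so a discrepancy between them could not be put down to the missing-data method alone.

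**Working it through.** **1. The plan's own figure.** Protocol 14.3 gives 80% power for a 6.5% difference with SD 9.02% and 30 per group. With two-sided alpha 0.05 (sidedness is not stated), SE = 9.02 × √(2/30) = 2.329, and power = Φ(6.5/2.329 − 1.96) = Φ(0.831) = 79.7%, or 78.4% by the noncentral t. The stated figure reproduces.

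**2. Who contributes.** A mixed model was fitted to one simulated data set of 60 in which 6 were last seen at month 3. With months 6 and 12 as the response it used 54 participants. With months 3, 6 and 12 it used all 60.

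**3. Precision, random loss.** Let q be the fraction of each arm lost between months 3 and 6, with no later loss, and ρ the month 3 to month 12 correlation. Neither is in the documents. Protocol 14.3 expects overall drop-out below 20%, without timing. In large samples:
- months 6 and 12 only: V0 = 2σ²/[n(1 − q)]
- months 3, 6 and 12: V1 = V0 × (1 − qρ²)

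For q = 0.05 and ρ = 0.6, 1 − 0.05 × 0.36 = 0.982, a 1.8% reduction. For q = 0.10 and ρ = 0.8, 1 − 0.10 × 0.64 = 0.936, a 6.4% reduction. With σ = 9.02, n = 30 and a 6.5% difference:

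| q | ρ | SE without month 3 | SE with month 3 | Power without | Power with |
|---|---|---|---|---|---|
| 5% | 0.6 | 2.389 | 2.368 | 77.6% | 78.4% |
| 10% | 0.6 | 2.455 | 2.410 | 75.4% | 76.9% |
| 10% | 0.8 | 2.455 | 2.375 | 75.4% | 78.1% |
| 20% (upper bound) | 0.7 | 2.604 | 2.473 | 70.4% | 74.8% |

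**4. Bias, if drop-out depends on month-3 change.** This is an assumption. Take logit(drop-out) = a − b × (month-3 change), with the same a and b in both arms and a set to give the stated overall loss. Assumed means are −5 at month 3 and −14 at month 12 on placebo, and −1 and −3.4 on zoledronic acid, so the true month-12 difference is 14 − 3.4 = 10.6 points. The error in an arm's month-12 mean when month 3 is ignored is ρ × (σ12/σ3) × (mean month-3 change among those who stay − mean among all). The shortfall is the placebo error minus the zoledronic acid error. σ12 is either 9.02, the plan's conservative SD, with σ3 = 4, or 5.08, the largest total-hip SD in Table 2, with σ3 = 4 × 5.08/9.02 = 2.25.

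| σ12 | Overall loss | b = 0.15, ρ = 0.6 / 0.8 | b = 0.30, ρ = 0.6 / 0.8 |
|---|---|---|---|
| 5.08 | 5% | 0.03 / 0.04 | 0.10 / 0.13 |
| 5.08 | 10% | 0.05 / 0.07 | 0.18 / 0.24 |
| 9.02 | 5% | 0.09 / 0.11 | 0.27 / 0.36 |
| 9.02 | 10% | 0.16 / 0.21 | 0.46 / 0.62 |

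The errors in the two arms go the same way and partly cancel. In the last cell they are 1.06 and 0.44, leaving 0.62. Every shortfall is toward no effect. The largest is 0.62/2.455 = 0.25 of a standard error. Under this mechanism the model with month 3 has no such bias.

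**5. The sensitivity analysis.** It keeps these participants, but centring months 6 and 12 on the month-3 value assumes no further average change. Protocol 1.1 places the greatest loss in the first 6 to 18 months after injury. It therefore does not stand in for a likelihood model that includes month 3.

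**The case against.** The case for leaving the plan alone has real force.

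- **Few are affected.** A reader might infer that everyone lost after month 3 is dropped, or dropped from every analysis. Neither holds. One later DXA, at month 6 or 12, keeps a participant in, including those censored at the month-6 safety cut-off. The imputation analysis keeps the rest.
- **The drop-out mechanism is not shown.** A reader might infer that month-3 bone loss drives early drop-out. The documents do not say so. Treatment is blinded, the bone-loss action point is month 6, and the attendance obstacles they name are residence and transport. WISCI and baseline aBMD, already in the model, may absorb part of any link; the calculation above leaves them out.
- **Month 3 will be incomplete.** Participants with transport problems may have no month-3 scan to recover, so the gains above are on the favourable side.
- **The imputation wording may be harmless.** It is tempting to say that imputed month-3 values feed no model. That goes too far. SAP, Exploratory Analyses, models markers and CT at month 3, and the Missing Data section could be read as general.
- **The statement in Diagnostics can be read narrowly,** as saying only that there is no listwise deletion among the modelled visits.
- **Adding a visit could change the test.** Primary analyses names an interaction over the modelled visits and no month-12 contrast.

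These points limit the size and wording of the concern. The last shapes the fix. None gives a reason to omit an outcome already scheduled, and the SAP states none.

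**Conclusion.** The concern holds in a limited form. The primary maximum-likelihood analysis leaves out participants whose only post-baseline DXA is at month 3. The SAP does not say so; it follows from the choice of visits, and it is at odds with the plain reading of Diagnostics.

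The effect is small: about 1% to 7% of the variance of the month-12 difference (1.8% to 6.4% by the formula), and a possible bias toward no effect of about 0.03 to 0.6 points on 10.6. Both ranges rest on assumed correlations of 0.6 to 0.8 and 5% to 10% lost between months 3 and 6. The bias also needs drop-out to depend on month-3 loss. Beside the effect of d ≥ 3.9 that Protocol 14.3 takes from the pilot data, this is unlikely to change the primary conclusion. The change is worth making because it uses data already scheduled and brings the model into line with the SAP's own statement.

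**What to change.** In SAP, Primary analyses, and the matching summary rows:

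1. Fit months 3, 6 and 12 as repeated responses, with group, visit and group-by-visit terms and an unstructured covariance.
2. Name the month-12 group difference as the primary contrast, so that the added visit does not change the hypothesis tested. This matches the one-year primary endpoint in Protocol 2.2. The fixed sequence from total hip to femoral neck can stay.
3. State that missed month-3 scans are not imputed in the likelihood model; under missing at random they need not be.
4. Report by arm how many participants have month 3 as their only post-baseline DXA.

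If the sponsor prefers months 6 and 12, the SAP should state the exclusion and its reason, and reword Diagnostics and Missing Data to match.

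No new data are needed. The cost is a rewritten paragraph and table rows, which should be settled before unblinding. Participants with no post-baseline DXA through month 12 would still add nothing under either model.

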1.1. Rationale

Spinal cord injury results in acute bone loss which is rapid and profound.

Spinal cord injury (SCI) results in marked acute loss of bone, primarily limited to those bony structures that are below the level of the neurologic lesion and non-weight-bearing, with little or no loss of bone at the spine and in bony structures that are supraspinal.^{1,2} The bone loss occurs rapidly, with the greatest decrease in bone density observed during the first 6-18 months after spinal cord injury, and is profound in magnitude, commonly being in the range of 15-30% at the hip, and potentially even higher at sites of less weight-bearing and of greater trabecular content below the hip.^{1,2} The degree of bone loss has been shown to be highly dependent on the degree of loading, with individuals having incomplete motor lesions and capable of some degree of weight-bearing having less bone loss than those with motor complete lesions.³ Lower extremity bone loss is similar in paraplegics and quadriplegics with similar motor function loss; upper extremity bone mass is unaffected in paraplegics but variably affected in quadriplegics, dependent on the degree of impairment of upper extremity function⁴. Age, weight and gender are important determinants of bone loss.³ Initially, bone mineral density (BMD) decline is reported to be most marked in areas rich in trabecular bone, with relative sparing of cortical bone ^{2,5-8} though recent studies from our group indicate significant acute loss of cortical bone as well ⁹ This enhanced rate of bone loss can be observed for between 2 and 5 years after acute SCI, at which time a new steady state is reached and bone resorption and bone formation become once again tightly coupled, but now at a new “set point” with bone mass that is 30-50% below the level prior to the injury.^{2,5-7} After this point in time, there is a much reduced rate of bone loss, with other secondary causes of bone loss, e.g., estrogen withdrawal, endocrinopathies, being potentially important contributors to further changes in bone status.

Loss of bone mass after acute SCI is paralleled by a marked decrease in bone strength.

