4.1.1. Inclusion Criteria

- In-patient at RIC/SRAlab or an outpatient who was recently discharged from RIC/SRAlab
- Males and females
- Age ≥ 18 years
- Medically stable in the opinion of subject's physiatrist
- SCI within 120 days of screening
- SCI with inability to ambulate independently (defined as walking more than 15-50 feet to perform normal activities of daily living such as walking to/from the bathroom with or without any assistive devices such as a walker and/or braces) or ASIA Impairment Scale (AIS) A, B, or C, at time of study entry
- Capable of positioning to have DXA performed
- Able to tolerate acetaminophen
- No known endocrinopathies (diabetes type 1 or 2, treated thyroid conditions can be included)
- Normal serum TSH and/or T4 levels
- Normal 25-OH vitamin D levels (≥ 20 ng/ml while not on supplemental vitamin D or ≥ 15 ng/ml while taking at least 1,000IU vitamin D daily) at baseline (subjects may be depleted)
- Normal calcium levels
- Normal renal function (creatinine < 2.0 mg/dl) and estimated creatinine clearance > 35 mL/min
- Well hydrated with adequate intake of liquids
- Able to return for all follow-up visits depending on ease of access to SRAlab post-discharge
- Capable of reading and understanding informed consent document
- Females of childbearing potential must be willing and able to use an effective method of contraception or practice abstinence throughout the course of the study.

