## ***Secondary analyses***

Secondary analysis will be divided into three main sections:

- a) Effect of functional capacity (WISCI) on aBMD of total hip and femoral neck percent-change; A secondary interaction analysis will be performed for the primary endpoint, exploring the effect of WISCI. The interaction of treatment with WISCI score will be fitted as a fixed effect (in addition to the WISCI score itself), with the resulting estimated treatment differences being shown for continuous scores of the WISCI scale.
- b) Secondary endpoint analysis at 12 months;

The primary analysis described above will be applied for all the three key secondary endpoints at 6, and 12 months visits, with the fixed sequence order described above. Appropriate p-values adjustments to compensate for a possible increased risk in Type I errors due to multiple secondary outcomes measurements will be done using a stepwise Dunnett procedure. All reporting will include both adjusted p values and raw effect sizes.

c) Primary and secondary endpoint analysis at 24 months.

Primary endpoint (total hip and femoral neck aBMD, measured by DXA) and secondary endpoints will be analyzed at 24 months. Here, we will study 4 groups of patients: 24 months of treatment, 24 months of no-treatment, switch from treatment to placebo at 12 months, switch from placebo to treatment at 12 months. A linear mixed model with the four groups, controlling for Baseline aBMD at the hip and ambulatory status measured by WISCI will be fitted to predict percent-change from baseline for each endpoint.

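### The primary and 24-month models leave out motor completeness at entry, which the protocol ties to bone loss, and so may give up some precision

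*SAP*

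**What the plan says.** The SAP (Primary analyses) lists the model terms as "Baseline aBMD at the total hip and femoral neck, study visit, ambulatory status measured by WISCI", followed by the interaction of WISCI with visit. The four-group 24-month model (SAP, Secondary analyses, item c) is described as "controlling for Baseline aBMD at the hip and ambulatory status measured by WISCI". The Analysis Plan Summary repeats the same set in nearly every row: "Baseline total hip aBMD, visit, WISCI score; (subjects as random effects"; the first row differs only in naming the femoral neck baseline as well. No SAP model contains AIS grade, motor completeness or time since injury.

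Protocol 1.1 describes "individuals having incomplete motor lesions and capable of some degree of weight-bearing having less bone loss than those with motor complete lesions". It also gives a time course, "with the greatest decrease in bone density observed during the first 6-18 months after spinal cord injury", and adds "Age, weight and gender are important determinants of bone loss".

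Protocol 4.1.1 admits people who cannot walk independently, or who are AIS A, B or C, with "SCI within 120 days of screening". Protocol 3.4 describes blocked 1:1 randomisation at entry and again at 12 months, with no stratification factor.

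**The concern.** The protocol itself names motor completeness as related to how much bone is lost. Entry spans complete and incomplete lesions, and neither the design nor the model accounts for the difference. Any variation in bone loss that goes with motor completeness, beyond what baseline aBMD and WISCI explain, therefore stays in the error term. With 30 per arm in year 1 and at most 15 per group in year 2, a covariate fixed before treatment is one of the few cheap ways to tighten the estimates. Hypotheses 1b to 1d rest on the small year-2 groups, so they have the most to gain.

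WISCI is only a partial substitute. Many entrants will be unable to walk independently, so entry scores may lie near the bottom of the scale; that is an inference, as no WISCI distribution is given. WISCI is collected at each visit and the SAP does not say which value enters the model. If it is the visit value, it is measured after randomisation. AIS at entry is not.

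**Working it through.** **The plan's own figure.** Protocol 14.3 gives SD 9.02%, 30 per group and 80% power for 6.5 points. Taking two-sided alpha 0.05 and the normal approximation, SE = 9.02 × √(2/30) = 2.329; 6.5/2.329 = 2.791; Φ(2.791 − 1.96) = 79.7%. The stated figure reproduces. For year 2 (15 per group, 9 points), SE = 9.02 × √(2/15) = 3.294; 9/3.294 = 2.733; Φ(2.733 − 1.96) = 78.0% against a stated 80%.

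**Cost and gain of k covariates.** With N participants in g groups, and covariates that explain an extra share R² of the variance, the expected variance ratio is about (1 − R²) × (N − g − 1)/(N − g − k − 1). For k = 2 the last factor is 57/55 in year 1 (N = 60, g = 2) and 55/53 in the four-group 24-month model (N = 60, g = 4). The documents give no R², so it is an assumption and the range starts at zero. Each power is Φ(z/SE ratio − 1.96), with z = 2.791 or 2.733.

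| Extra R² | SE ratio, year 1 | Power, 6.5 points | SE ratio, 24 months | Power, 9 points |
|---|---|---|---|---|
| 0 | 1.018 | 78.3% | 1.019 | 76.5% |
| 0.05 | 0.992 | 80.3% | 0.993 | 78.6% |
| 0.10 | 0.966 | 82.4% | 0.966 | 80.7% |
| 0.20 | 0.911 | 86.6% | 0.911 | 85.1% |
| 0.30 | 0.852 | 90.6% | 0.852 | 89.4% |

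The comparison is with 79.7% and 78.0% without the two covariates. These powers start from the raw SD, which takes no credit for baseline aBMD or WISCI, so they show direction and scale only.

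**Break-even R².**
- Two covariates, year 1: 1 − 55/57 = 0.035.
- Two covariates, four-group model: 1 − 53/55 = 0.036. With 20% dropout (N = 48): 1 − 41/43 = 0.047.
- Two covariates, two groups of 15 analysed alone: 1 − 25/27 = 0.074.
- Motor completeness alone, year 1: 1 − 56/57 = 0.018.

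**Chance imbalance.** Assume that 50, 60 or 70% are motor-complete and hold that total fixed. The hypergeometric chance of a difference of 20 percentage points or more is 20, 19 or 16% at 30 v 30 (30, 36 or 42 of 60). At 15 v 15 it is 47, 26 or 43% (15, 18 or 21 of 30); these are uneven because the counts are small. Such imbalance is not likely in year 1, but it is a material risk in year 2.

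**Where the gain matters.** The left total hip pilot difference is 13.83 − 3.40 = 10.43 points. At SD 9.02, year-1 power is Φ(10.43/2.329 − 1.96) = 99.4%. At 15 per group it is Φ(10.43/3.294 − 1.96) = 88.6%, in line with the stated 88%.

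**The case against.** The best defence is that the main mechanism is already in the model. The rationale ties bone loss to loading, and its sentence on motor completeness joins lesion type to weight-bearing. Protocol 3.6 chose WISCI because it reflects activity that loads bone, and every SAP efficacy model described carries it. What AIS would add after WISCI is unknown. This stands, and it is why the range of R² must start at zero.

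Several stronger readings are tempting but not supported:
- **That WISCI is useless because entry selects non-walkers.** The criterion is an either/or, so an AIS C participant who walks can enter. Scores may cluster low; the documents do not show that they do.
- **That time since injury has equal support.** The rationale gives a time course over 6 to 18 months, not a gradient within the first 120 days. The link is inferred. The same section names age, weight and gender more directly, and those are omitted too.
- **That the comparison is biased.** Randomisation protects it; chance imbalance costs precision.
- **That the change is free and both values are known at eligibility.** AIS is one branch of an either/or criterion and is not named in Protocol 3.6 or the visit schedule. Days to first infusion are fixed only at the infusion visit.
- **That the equivalent of 7, 21 or 38% more participants is being lost.** These are 1/0.933, 1/0.829 and 1/0.725, from assumed R² of 0.1, 0.2 and 0.3. At zero there is a small loss.

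**Conclusion.** The point holds as a missed opportunity for precision. Motor completeness is named in the protocol as related to bone loss, is not stated to be balanced by design and is absent from both models. With two added covariates at N = 60, the standard error would change by between about +2% and -15% for an extra R² of 0 to 0.3. The break-even is near 0.035, or up to about 0.07 if a 15 v 15 comparison is analysed alone. All of this rests on the assumed R² beyond baseline aBMD and WISCI, and on entry AIS being available for everyone. The year-1 total hip test does not depend on the change if the true effect is near the pilot difference. The benefit falls on the year-2 comparisons (Hypotheses 1b to 1d), on smaller effects and on a sample reduced by dropout.

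**What to change.** First confirm that AIS at entry is recorded for all randomised participants. Then, before unblinding, amend the SAP so that the primary model, the 24-month model and the Analysis Plan Summary include entry motor completeness (AIS A/B against C/D) as a fixed effect. Days from injury to first infusion, as a continuous term fixed before treatment, may be added as a second covariate; the SAP should say that its support is inferred from the time course in the rationale. Keep the list to these and do not select covariates from the data.

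The cost is SAP wording, a check of the AIS records and up to 2 degrees of freedom, with no new visits or participants. Because the SAP overview describes randomisation and imaging in the past tense, the amendment should be dated and should document that it was made blind to treatment. If the covariates explain almost nothing, the standard error rises by about 2%.
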